9 SURGICAL AND MEDICAL HISTORY

Surgical and medical history will be coded according to the Medical Dictionary for Regulatory Activities (MedDRA), version 22.0.

Surgical and medical history will be summarized for each dosing regimen by system organ class (SOC) and preferred term (PT) based on the Safety population. A patient who experienced the same surgical and medical history event multiple times within the same SOC will be counted only once for that SOC. Similarly, a patient who experienced multiple surgical and medical history events within the same PT will be counted only once for that PT. Surgical and medical history events will be sorted alphabetically by SOC and within each SOC, the PT will be presented by decreasing order.

A listing of all surgical and medical history events will be provided. All surgical and medical history for each patient in the Safety population will be included in a data listing.

10 PRIOR AND CONCOMITANT MEDICATIONS

Medications will be coded according to the World Health Organization Drug Dictionary (WHO-DD), March 2019 B3.

Prior medications are defined as any medication started and discontinued prior to the first dose of study drug. Concomitant medications are defined as all medications taken after the first dose of study drug, including dose who started prior to the first dose of study drug and continued past that date. See Appendix 3 for handling of completely or partially missing dates for prior and concomitant medications.

Frequency and percentage of prior and concomitant medications will be tabulated by Anatomical Therapeutic Chemical (ATC) term level 2 and preferred drug name by dosing regimen based on the Safety analysis population. A patient who took the more than one medication within the same medication ATC level 2 will be counted only once for that ATC level 2. Similarly, a patient who took more than one medication within the same preferred drug name will be counted only once for that preferred drug name.

A listing of all prior and concomitant medications will be provided.

	STATISTICAL ANALYSIS PLAN, Final v1.0
Protocol Number CP543.2003	Sponsor: Concert Pharmaceuticals, Inc.

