#### 8.5. **Concomitant Medications and Procedures**

All medications, including over-the-counter therapies (e.g., vitamins, herbal, and nutritional supplements), taken one month prior to Screening and through the Follow-up Visit will be recorded in the patient's source documentation and documented in the eCRF.

Any concomitant medication deemed necessary for the wellbeing of the subject may be given at the discretion of the Investigator. Use of medications that are prohibited per protocol may require patient withdrawal from the study.

The following treatments and procedures are not permitted during the study:

- Medications that may affect hair regrowth or immunosuppression (such as: corticosteroids administered orally, by injection, or applied to areas of skin affected by alopecia; topical application of anthralin, squaric acid, diphenylcyclopropenone, or minoxidil:
- Treatment with systemic immunosuppressive medications including but not limited to methotrexate, cyclosporine, and azathioprine; chloroquine derivatives; Janus kinase inhibitors (ruxolitinib, tofacitinib, etc), etanercept; or biologics (adalimumab, atlizumab, canakinumab, certolizumab, fontolizumab, golimumab, infliximab, mepolizumab, rituximab, secukinumab, tocilizumab, ustekinumab);
- Use of strong CYP3A4 inhibitors (such as, but not limited to clarithromycin, conivaptan, grapefruit juice, indinavir, itraconazole, ketoconazole, lopinavir/ritonavir, mibefradil, nefazodone, nelfinavir, posaconazole, saquinavir, telaprevir, telithromycin, voriconazole, or fluconazole);
- Use of strong CYP3A4 inducers (such as, but not limited to barbiturates, carbamazepine, efavirenz, glucocorticoids, modafinil, nevirapine, oxcarbazepine, phenobarbital, phenytoin, pioglitazone, rifabutin, rifampin, St. John's Wort, or troglitazone).

• PUVA treatment, UV-B phototherapy (including tanning beds) or excimer laser, excessive sun exposure or use of tanning booths.

• Obtain hair transplants.

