2 STUDY OBJECTIVES AND ENDPOINTS

OBJECTIVES	ENDPOINTS
Primary	
To compare the efficacy and tolerability of a 24 mg total daily dose of CTP- 543 utilizing two different	Primary efficacy endpoint in each dose regimen: • Relative change in Severity of Alopecia Tool (SALT) score for each dose regimen from Baseline at Week 24.
dosing regimens in adult	Tolerability endpoints in each dose regimen:
patients with chronic, moderate to severe alopecia areata.	• Adverse events (AEs), vital signs, concomitant medications, clinical laboratories, and electrocardiogram (ECG) results, as well as physical examinations
Secondary/Exploratory	
To assess the proportion of	Secondary efficacy endpoints in each dose regimen:
patients achieving defined threshold reductions in SALT score, and for	• Proportion of patients achieving at least a 90%, 75%, and 50% reduction in SALT score from Baseline at Weeks:
patients to assess their	o 4, 8, 12, 16, 20, and 24 in the Treatment Period
eyebrows, hair coverage and hair coverage quality.	 Absolute change in SALT scores from Baseline at Weeks: 4, 8, 12, 16, 20, and 24 in the Treatment Period

	STATISTICAL ANALYSIS PLAN, Final v1.0	
Protocol Number CP543.2003	Sponsor: Concert Pharmaceuticals, Inc.	

OBJECTIVES	ENDPOINTS	
	Relative change in SALT scores from Baseline at Weeks:	
	o 4, 8, 12, 16, and 20 in the Treatment Period	
	 Change in satisfaction of hair coverage as reported by the patient from Baseline to Weeks 8, 12, and 24 	
	Exploratory efficacy endpoints in each dose regimen:	
	• Change in patient's eyebrows as measured by the patient's Visual Analog Scale (VAS) from Baseline to Weeks 12 and 24	
	 Change in satisfaction of hair coverage quality as reported by patient from Baseline to Weeks 8, 12, and 24 	

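### The concomitant-medication table pools drugs continued from before first dose with drugs started on treatment, so it is a weak tolerability measure; a by-regimen table of new starts is missing (minor)

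*SAP*

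**What the plan says.** SAP section 2 gives the tolerability endpoints under the primary objective as "Adverse events (AEs), vital signs, concomitant medications, clinical laboratories, and electrocardiogram (ECG) results, as well as physical examinations". Protocol 11.2.2 has the same list.

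SAP section 10 splits medications in two. On one side, "Prior medications are defined as any medication started and discontinued prior to the first dose of study drug". On the other, "Concomitant medications are defined as all medications taken after the first dose of study drug, including dose who started prior to the first dose" and were continued beyond it (the word dose before who is evidently a slip for those). For the table, "Frequency and percentage of prior and concomitant medications will be tabulated by Anatomical Therapeutic Chemical (ATC) term level 2", together with preferred drug name, by regimen in the Safety population. Within a class, a patient with more than one "medication ATC level 2 will be counted only once for that ATC level 2", and the same rule applies to each preferred drug name. Finally, "A listing of all prior and concomitant medications will be provided".

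Protocol 8.5 sets a wide collection window: "All medications, including over-the-counter therapies (e.g., vitamins, herbal, and nutritional supplements), taken one month prior to Screening" through the Follow-up Visit. SAP Appendix 3 imputes a completely missing start date to the date of first dose. It does the same for a date with only the year, or only month and year, when these match the first dose. SAP 5.1 treats medications starting on the first-dose date as post-Baseline.

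**The concern.** As a tolerability measure, concomitant medication use is informative to the extent that one regimen leads patients to start more drugs than the other. Use that began before randomisation and simply continued cannot reflect either regimen. Yet SAP section 10 puts both in the same cell, and no other planned table separates them.

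The other tolerability endpoints are anchored to Baseline or first dose. Treatment-emergent adverse events need onset on or after first dose (SAP 13.1). Laboratory values, vital signs and ECG intervals are summarised as change from Baseline, and potentially clinically significant laboratory values count only if absent at Baseline (SAP 13.2, 13.3, 13.5). Physical examination reports deteriorations (SAP 13.4). Concomitant medications are the exception.

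Some ongoing use is to be expected. The inclusion criteria list hormonal contraceptives, stable for at least 4 weeks before Baseline. Inhaled and intranasal corticosteroids are allowed, and vitamins and supplements are recorded.

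The once-per-class count adds to the problem. A patient already taking one drug in a class who starts a second on study adds nothing to the ATC level 2 row. At about 30 patients per arm, chance imbalance in ongoing use can be as large as the signal of interest.

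**Working it through.** The documents give no figure for medication use, so there is no planned number to reproduce. The following is an illustration for one ATC level 2 row.

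**Inputs**
- n = 30 per regimen (SAP 3.1, approximate).
- New-start rates r: 10% vs 30%. Assumed.
- Share b already using the class at Day 1 and continuing: 20%, 40% or 60%, equal in expectation in both arms and independent of r. Assumed.

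**Planned table (any use after first dose).** Expected rate = b + (1 − b)r, so the expected difference is (1 − b) × 20 points.
- b = 20%: 28% vs 44%, difference 16 points
- b = 40%: 46% vs 58%, difference 12 points
- b = 60%: 64% vs 72%, difference 8 points

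The standard deviation of the chance between-arm difference in ongoing use is √(2b(1 − b)/30), or 10.3, 12.6 and 12.6 points.

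**New-start table, all patients in the denominator.** Two cases bracket what existing users do.
- They start new drugs in the class at the same 10% and 30%: the row shows 10% vs 30%, and the full 20 points survive.
- They start nothing new in the class: the expected rate is (1 − b)r, giving 8% vs 24%, 6% vs 18% or 4% vs 12%. The difference is again 16, 12 or 8 points, but the noise from ongoing use is gone.

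**New-start rate among patients not using the class at Day 1.** The expected difference is 20 points whatever b is, on about 30(1 − b) = 24, 18 or 12 patients per arm.

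**Difference divided by its standard error**, with SE = √[p₁(1 − p₁)/n + p₂(1 − p₂)/n]:

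| b | Planned table | New starts, existing users start nothing | New starts among non-users |
|---|---|---|---|
| 20% | 16.0/12.2 = 1.31 | 16.0/9.2 = 1.73 | 20/11.2 = 1.79 |
| 40% | 12.0/12.8 = 0.94 | 12.0/8.2 = 1.46 | 20/12.9 = 1.55 |
| 60% | 8.0/12.0 = 0.67 | 8.0/6.9 = 1.15 | 20/15.8 = 1.26 |

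**Chance that the arm with more new starts shows no excess, or fewer users.** With A the 10% arm and B the 30% arm, this is Σₓ P(X_A = x) P(X_B ≤ x), both binomial with n = 30 and the rates above:

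| b | Planned table | New starts, existing users start nothing | New starts, existing users start at the same rates |
|---|---|---|---|
| 20% | 12% | 6% | 3% |
| 40% | 21% | 10% | 3% |
| 60% | 30% | 18% | 3% |

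**Start dates.** Take a patient first dosed in 2019 who has long used a drug whose start is recorded only as 2019. Appendix 3 sets that start to the first-dose date, and SAP 5.1 makes it post-Baseline. A new-start table built on imputed dates would count it as new. A completely missing start date has the same result, as does a date lacking only the day when month and year match first dose.

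**The case against.** The definition is explicit and does its stated job of separating prior from concomitant drugs, so there is no contradiction or error in it. Tolerability does not rest on this table. Treatment-emergent events are tabulated by system organ class, preferred term, severity and relationship. Serious events are summarised, as are events leading to discontinuation or interruption, and laboratory, vital-sign and ECG data are shown by regimen. SAP section 13 rules out inference on any safety endpoint, so no formal decision turns on a medication rate. The masking is mainly at ATC level 2: a new drug with a different preferred name gets its own row, and every medication is listed by patient. All of this stands, and it makes the point minor.

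It does not remove the gap. A descriptive table is still read as a comparison, and a patient listing is not a comparison of regimens. Protocol 10.2.5 has the investigator record whether treatment was given for an event, but no summary of that is planned.

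A reader might go further and infer that the table counts every drug a patient took before first dose, or that it mostly shows baseline use. The documents support neither. Drugs started and stopped before first dose are classed as prior. Ongoing users exceed half of those counted only if b > r/(1 + r), which is 9.1%, 16.7% or 23.1% for new-start rates of 10%, 20% or 30%. No baseline rate is given from which to judge this.

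Nor does a new-start table always restore the full difference. It does so only if existing users start new drugs in the class at the same rates, or if the rate is taken among non-users.

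**Conclusion.** The point holds as a minor reporting weakness. A named tolerability endpoint is summarised in a way that mixes ongoing use with new starts, and nothing planned separates them by regimen. At ATC level 2 the expected difference in new use shrinks by the factor (1 − b) for any ongoing use b above zero, and chance imbalance in ongoing use adds noise.

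Under the assumed rates, a new-start table cuts the chance of a null or reversed picture from 12%, 21% or 30% to 6%, 10% or 18% in the less favourable case, and to 3% in the more favourable one. These probabilities rest on assumed usage rates, equal expected ongoing use in the two arms, and independence of ongoing use and new starts. The direction of the effect does not depend on the particular rates chosen. The primary efficacy analysis is untouched.

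**What to change.** In SAP section 10:

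1. Keep the present definition of concomitant medication, but split it into drugs ongoing at first dose and drugs started on or after first dose.
2. Tabulate the second group by ATC level 2, preferred drug name and regimen as the tolerability summary. Show the first group as background.
3. For ATC level 2 rows, also give the new-start rate among patients not already using that class at Day 1, with its denominator.
4. Classify as ongoing any drug recorded as in use at Screening or before dosing on Day 1, and not stopped before first dose, when its start date is completely or partially missing. Say that this rule overrides the Appendix 3 imputation for this table. Protocol Table 1 already has medications collected at both visits.

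The cost is one paragraph, one extra table and a date-classification rule to program and check, all from data already collected. It should be settled before database lock and unblinding.

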11 STUDY TREATMENT EXPOSURE AND TREATMENT COMPLIANCE

A summary of exposure to study drug (days) will be presented by dosing regimen based on the Safety analysis population. Exposure to study drug, in days, will be computed as follows:

[(Date of last dose of study drug – Date of first dose of study drug) + 1]

Compliance with study drug (%) will be calculated as follow:

Number of tablets taken x 100%
Total number of tablets planned to be taken

where the number of tablets taken is defined as the total number of tablets dispensed minus the total number of tablets returned, and total number of tablets planned to be taken is defined as the exposure to study drug multiplied by the number of planned tablets per dose (i.e., 2).

Descriptive statistics for the compliance to study drug will be presented by dosing regimen based on the Safety population. Frequency distribution will also be presented for the following categories: < 80%, 80% - 120%, and > 120%.

Exposure and compliance will be displayed in a listing of study treatment administration.

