#### 7.3. **Patient Withdrawal Criteria**

All patients are free to withdraw from participation in the study at any time, for any reason, and without prejudice. The Investigator must withdraw any patient from the study if the patient requests to stop participating in the study. The Investigator, Sponsor, or its designee may remove a patient from the study at any time and for any reason if they believe the safety of the patient or the integrity of the data are at risk. In addition, patients should be withdrawn if they:

- Experience an intolerable adverse event
- Require a medication that is prohibited by the protocol
- Do not follow guidelines specified in the protocol (i.e., e.g. patient may be withdrawn if noncompliant with protocol procedures or study treatment administration)
- Any medically appropriate reason or significant protocol violation, in the opinion of the Investigator
- Are lost to follow up
- Female patient becomes pregnant

Patients who withdraw or are withdrawn from the study will not be replaced.

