### 8.3. Treatment Compliance

At each scheduled study visit after randomization, the Investigator or designee will interview the patient regarding treatment compliance and compare the number of dispensed versus returned study drug tablets. Patients should strive for 100% compliance with the daily dosing schedule. Retraining on treatment compliance should occur for patients with less than 80% or over 120% compliance at any visit and the Sponsor should be notified.

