3 STUDY DESIGN

3.1 Overall Design

This is a randomized, parallel-group, multicenter study to evaluate the efficacy and tolerability of two dosing regimens of CTP-543 (12 mg twice daily [BID] vs 24 mg once daily [QD]) in adult patients with chronic, moderate to severe alopecia areata. Patients will be between 18 and 65 years of age and experiencing an episode of alopecia areata lasting at least 6 months and not exceeding 10 years, with at least 50% hair loss as measured by the Severity of Alopecia Tool (SALT) at Screening and Baseline, and are not concurrently being treated for alopecia areata with other treatments that might affect hair regrowth or immune response. Up to approximately 75% of alopecia areata patients with alopecia totalis or universalis, and no more than 10% of patients with alopecia ophiasis will be enrolled.

A full list of the inclusion and exclusion criteria can be found in Sections 7.1 and 7.2 in the CP543.2003 Protocol.

Patients may be screened up to 28 days prior to initiation of study drug. The Treatment Period is a 24-week dosing period where patients will be randomized to receive either 12 mg BID or 24 mg OD of CTP-543.

[figure not shown]
[figure not shown]

Figure 1: Study Design

Patients will provide informed consent prior to completing any screening procedures. Patients meeting screening criteria will continue to the Day 1 Randomization Visit for review of eligibility and Baseline assessments. Patients meeting all eligibility criteria will be randomized to receive either 12 mg BID CTP-543 or 24 mg QD CTP-543 in a 1:1 ratio. Approximately 60 patients are planned to be randomized in the study (i.e., approximately 30 patients per dosing regimen).

Patients will take the first dose of study drug in the clinic on Day 1 and will be instructed to take study drug every 12 hours. To minimize the bias in the evaluation of study endpoints, patients, investigators, and site personnel will be unaware of the active drug dosing regimen by administering 2 x 12 mg tablets and 2 x placebo tablets 12 hours apart from each other for the 24 mg QD study drug. Patients should dose study drug in the clinic on all Study Visit Days after clinical laboratory blood draws are completed.

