Appendix 1 provides a description of the procedures planned at each visit.

3.2 Treatment Regimens

CTP-543 will be dosed orally as tablets. Doses and frequency will be allocated as follows:

- 12 mg BID CTP-543 (1 x 12 mg and 1 x placebo tablet every 12 hours)
- 24 mg QD CTP-543 (2 x 12 mg in the mornings and 2 x placebo tablets in the evenings)

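### SAP 11 counts every unreturned tablet as taken, so a patient lost early, soon after a dispensing visit, can be reported as compliant or above 120% whatever was really taken

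*SAP*

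**What the plan says.** SAP 11 defines compliance as tablets taken over tablets planned, times 100.

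- **Numerator:** "where the number of tablets taken is defined as the total number of tablets dispensed minus the total number of tablets returned".
- **Denominator:** "the exposure to study drug multiplied by the number of planned tablets per dose (i.e., 2". Exposure is in days: "Date of last dose of study drug – Date of first dose of study drug) + 1".
- **Output:** descriptive statistics and the bands <80%, 80-120% and >120%, by regimen on the Safety population, plus a listing.

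SAP 3.2 gives the tablet load: "12 mg BID CTP-543 (1 x 12 mg and 1 x placebo tablet every 12 hours" in one arm and "24 mg QD CTP-543 (2 x 12 mg in the mornings and 2 x placebo tablets in the evenings" in the other, so 4 tablets a day in both.

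Protocol Table 1 schedules dispensing on Day 1 and at Weeks 4, 8, 12, 16 and 20. Accountability is scheduled at Weeks 4 to 20 and at Week 24/Early Termination. Under Protocol 8.3, at each visit "the Investigator or designee will interview the patient regarding treatment compliance and compare the number of dispensed versus returned study drug tablets". Protocol 7.3 lists among the withdrawal criteria patients who "Are lost to follow up". Protocol 8.4.5 requires reconciliation of all drug, recorded for each patient.

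Neither document says how the formula treats a pack that is never returned. SAP Appendix 3 imputes missing dates for adverse events and medications only, so an unknown last dose date has no rule either.

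**The concern.** A pack can be counted only if the patient brings it back. When it stays out, the numerator gains the whole pack, while the denominator gains days only up to the last recorded dose. The two then cover different periods, and the gap is widest when loss follows soon after dispensing and early in the study, because one pack is then a large share of all tablets planned.

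The primary objective compares efficacy and tolerability of two regimens, and compliance is the plan's summary of how each regimen was actually taken. With about 30 patients per arm, one patient in the wrong band moves that band by 1/30, about 3 percentage points. The patients affected are those who disappear, whose adherence is of most interest. The interview that sites already hold under Protocol 8.3 could inform these cases, but the SAP formula does not use it.

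**Working it through.** **Inputs from the documents.** 4 tablets a day (SAP 3.2); 24 weeks = 168 days ("The Treatment Period is a 24-week dosing period", SAP 3.1); six dispensings (Protocol Table 1); numerator, denominator and bands (SAP 11).

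**Assumptions, not in the documents.** 112 tablets per pack (28 days x 4) with no spares. The patient attends the Week *w* visit, returns the previous pack, receives a new one and is never seen again. The last dose is dated to that visit.

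**Benchmark.** The plan states no compliance result, but Protocol 8.3 sets 100% as the target. A fully adherent completer takes 168 x 4 = 672 tablets.

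- SAP 11 read literally: 672 / (168 x 2) = 200%.
- With 4 tablets per exposure day: 672 / (168 x 4) = 100%.

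Only the second reading returns the target, so the rest uses 4 a day. This isolates the numerator problem.

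**Loss just after Week *w*, true use *a*.** Exposure = 7w + 1 days. Planned = 4(7w + 1). Counted as taken = 28w·a + 112. The last column is the true use from which the report reaches 80%: (0.8 x planned - 112) / 28w.

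| Lost after | Planned | a = 100% | a = 70% | a = 50% | Reaches 80% from |
|---|---|---|---|---|---|
| Week 4 | 116 | 224/116 = 193% | 190.4/116 = 164% | 168/116 = 145% | any use |
| Week 8 | 228 | 336/228 = 147% | 268.8/228 = 118% | 224/228 = 98% | 31% |
| Week 12 | 340 | 448/340 = 132% | 347.2/340 = 102% | 280/340 = 82% | 48% |
| Week 16 | 452 | 560/452 = 124% | 425.6/452 = 94% | 336/452 = 74% | 56% |
| Week 20 | 564 | 672/564 = 119% | 504/564 = 89% | 392/564 = 70% | 61% |

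After Week 4 even zero use would be reported as 112/116 = 97%.

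**Later last dose within the interval.** The inflation shrinks. With 70% use and the second pack kept, a last dose on Day 35 gives 190.4/140 = 136%, and on Day 56 gives 190.4/224 = 85%.

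**Completer who keeps only the last pack.** Reported = (560a + 112)/672 = a + (1 - a)/6. True use of 50%, 60%, 70% and 75% becomes 58%, 67%, 75% and 79%, all still <80%. Only true use from 76% to just under 80% changes band. With 8 or 16 spare tablets per pack, 70% becomes 76.2% or 77.4%.

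**Effect of the remedy.** With the unreturned interval dropped from both parts and 4 tablets a day, the 70% user lost after Week 12 scores 235.2 / (84 x 4) = 70%. With the literal factor of 2, the same patient scores 235.2 / (84 x 2) = 140%.

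**The case against.** Comparing dispensed with returned tablets is the protocol's own method, and accountability is scheduled at every dispensing visit after Day 1. An attending patient therefore usually has only the latest pack outstanding. Early discontinuers are asked to attend a termination visit that includes accountability, and all drug must be reconciled. Details of returns sit in a Study Manual that is not available. All of this stands, and it narrows the problem to patients who miss that visit or withhold a pack. It does not remove it: reconciliation records a missing pack but does not change what the formula does with it.

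The table also shows the most extreme timing, and the number of patients concerned is unknown. Planning about 60 patients for 25 completers per group leaves 60 - 50 = 10 non-completers. That is an inference, not a stated allowance for loss to follow-up; the number keeping a pack could be anywhere from 0 to 10.

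The larger fault in the same sentence is the denominator. Read literally, days x 2 doubles every patient's value, and with everything returned only true use below 40% falls in the <80% band. This stands in full, and is why the two corrections belong together.

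A reader might infer that the regimen losing more patients would show the better compliance. The documents do not support this as a prediction: both arms take the same blinded number of tablets, and nothing in them points to unequal loss. It would be a consequence only if unequal loss occurred.

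**Conclusion.** The point holds in a limited form. For a patient lost early, soon after dispensing and with the pack unreturned, the SAP 11 value says little about true use: at 70% true use it runs from 164% (loss after Week 4) to 89% (Week 20). These figures rest on the assumed pack size, no spares, 4 tablets a day and a last dose dated to the visit.

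Two stronger readings are tempting. One is that anyone who keeps the last pack will look compliant; for a 24-week completer the inflation is only one sixth of the shortfall. The other is that under-use always leaves the <80% band; 50% use with loss after Week 16 or 20 stays below it, at 74% and 70%.

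The consequence is confined to the descriptive compliance table and listing, where a value such as 193% would be visible. Compliance enters no SALT estimate, and no compliance cut-off defines the mITT or Per Protocol population. The documents do not say whether it will inform the classification of major deviations. This is an inexpensive improvement to the SAP, not a threat to the primary result.

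**What to change.** In SAP 11:

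1. Compute compliance only over dispensing intervals whose pack was returned and counted, and drop an interval with an unreturned pack from both numerator and denominator.
2. Report by regimen the number of patients with unreturned drug, and list the interview information for the dropped intervals. The documents do not say that the interview yields a tablet count, so it should be listed, not entered in the formula.
3. In the same edit, reconcile the denominator (exposure days x 2 per dose) with the 4 tablets a day in SAP 3.2. Without this, step 1 does not restore the <80% band.

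The cost is SAP wording and minor programming. Some patients will have no compliance value for their last interval, and a patient who never returns a pack will have none at all. The remaining value describes only the counted intervals, so it may look better than a lost patient's use over the whole period; the count of patients with unreturned drug should be shown beside it.
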